Subjects will undergo clinical evaluations as outlined below on day 0, week 6 and week 12, which will include a subject questionnaire rating subjective parameters (Global Aesthetic Improvement Scale and Cosmetic Improvement Scale) and high resolution, standardized imaging (Canfield VISIA CR Gen 5 with 3DPrimos) to evaluate targeted fluorescence imaging of protoporphyrin-IX and coproporphyrin-III for measuring microbial activity, standard white light and polarized imaging for textural and topographical information, RBX® Red/Brown processing for measuring pigmentation, and 3D imaging with Primos for roughness and volumetric measurements. All subjects will have skin microbiome analysis performed from the face at baseline and week 12 unless they did not meet criteria (i.e., washed face 3-hours prior to clinical visit, which would shift the skin microbiome; or prior allergy to adhesives) or unless they decline. Skin microbiome analysis would be performed by skin swab and tape-stripping. Subjects (up to n=80) who are interested in being involved for a longer duration in the study will be followed to 26-week and 52-week time points for long-term analysis of topical HPE on facial and decolletage skin per subject preference. Subject renumeration will be provided for skin biopsies, and follow-up 26- and 52-week visits.

At the end of the study participants will be asked if they would like to participate in a video interview using an interview guide. Participants that don't continue use of the products after 12 weeks, will be given the option to return to the clinic for photos at 6 months and 12 months. These participants will be given another bottle of the study product.

We will use a zoom type platform and capture study participants thoughts and attitudes towards overall skincare routines and HPE (plated) TM SkinScience product. Each selected patient will be recorded in a 30-minute interview. The interviews will be transcribed, edited for patient testimonials (2–3-minute videos) and used in marketing and patient education materials.

Amendment 2X concentration study:

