Informed consent must be obtained with signing of the ICF prior to performing any study-related procedure.

Assessments during the screening visit will include:

- Demographic data
- Medical and surgical history
- Medication history
- Concomitant medication
- Concomitant procedures
- Physical examination

Based on the result of the screening visit and review of the eligibility criteria, the PI will assess each potential subject's eligibility for study inclusion. If the subject is found eligible, she can then be enrolled. The screening visit results will be recorded in the subject's electronic case report form (e-CRF) and the subject will be scheduled for a subsequent visit to complete additional baseline assessments,

Enrolled subjects will then initiate baseline visit (V0) at the same time during which they will complete their baseline assessments and initiate their treatment.

General assessment

- Baseline VISIA-CR imaging
- Photography
- Skin microbiome facial swab and tape-stripping (n=80 skin swab and tape-stripping)
- Skin biopsy (n=30)
 - o Left upper inner arm (untreated skin)

Treatment

- Treatment: Topical HPE twice daily for study duration.
- Study staff will demonstrate treatment application.
- Subject instructions and treatment log will be provided.
- Each subject will receive the first cosmetic kit, which will include gentle cleanser, unscented bar soap, HPETM product, SkinceuticalsTM CE Ferulic serum, sunscreen and moisturizer. A second cosmetic kit will be provided at week 6 visit.

• For questions, subjects will be provided contact email: [contact]

Visit 1: Follow-up at 6-weeks

- VISIA-CR imaging
- Photography
- Topical treatment jars will be weighed to ensure correct application amount.
- Subject treatment log will be reviewed.

Specific assessment (cosmetic evaluation questionnaires)

- Global Aesthetic Improvement Scale
- Cosmetic Improvement Scale

Treatment assessment

- Continuation of Topical HPE twice daily as indicated.
- Study staff will re-demonstrate treatment application.
- Each subject will receive their second cosmetic kit, which will include gentle cleanser, unscented bar soap, HPETM product, SkinceuticalsTM CE Ferulic serum, sunscreen and moisturizer.
- For questions, subjects will be provided contact email: [contact]

Visit 2: Follow-up at 12-weeks

- VISIA-CR imaging
- Photography
- Skin microbiome facial swab and tape-stripping (n=80 skin swab and tape-stripping)
- Skin biopsy (n=30)
 - Right upper inner arm (HPE)

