- Topical treatment jars will be weighed to ensure correct application amount.
- Subject treatment log will be reviewed.

Specific assessment (cosmetic evaluation questionnaires)

- Global Aesthetic Improvement Scale
- Cosmetic Improvement Scale

Treatment assessment

Continuation of topical HPE twice daily on the face and decolletage only as indicated for 20 subjects.

- Study staff will re-demonstrate treatment application.
- Each subject will receive their second cosmetic kit, which will include gentle cleanser, unscented bar soap, HPETM product, SkinceuticalsTM CE Ferulic serum, sunscreen and moisturizer.
- For questions, subjects will be provided contact email: [contact]

Visit 3 and 4: Long-term follow-up at 26- and 52-weeks. Cohort 2 (n= up to 80)

VISIA-CR imaging

- Photography
- Topical treatment jars will be weighed to ensure correct application amount.
- Subject treatment log will be reviewed.

Specific assessment (cosmetic evaluation questionnaires)

- Global Aesthetic Improvement Scale
- Cosmetic Improvement Scale

Figure 1: Study Summary

Face and decolletage (n=80)

Right dorsal hand (n=80)

Right inner arm (n=30)

HPE

. . . .

- Week 0
- · VISIA-CR imaging
- Photography
- · Skin microbiome

Week 6

- · VISIA-CR imaging
- Photography
- Questionnaires

Week 12

- · VISIA-CR imaging
- Photography
- Questionnaires
- Skin microbiome

Week 26 and Week 52

- VISIA-CR imaging
- Photography
- Questionnaires

HPE

Left dorsal hand (n=80)

Skinceuticals C.E. Ferulic

Week 0, 6 and 12

- VISIA-CR imaging
- · Photography
- Questionnaires

HPE – week 12 biopsy

Left inner arm (n=30)

Untreated – week 0 biopsy

Week 0

- Skin biopsy (untreated) Week 12
- Skin biopsy (HPE)

Table 1: Summary of Monitoring and Follow-Up Assessments

Assessment	Screening / Baseline Visit (Visit 0)	6 Weeks (Visit 1) (±4 Days)	12 Weeks (Visit 2) (±7 Days)	26 Weeks* (6 months) (Visit 3) (±14 Days)	52 Weeks* (12 months) (Visit 4) (±30 Days)
Informed Consent and HIPAA Authorization	X				_
Questionnaires and Assessments	All Encounters				
Skin biopsy*	X		X	_	_
Microbiome analysis (skin swab and tape-stripping)	X	_	X	_	_
VISIA-CR imaging	X	X	X	X	X
Photography	X	X	X	X	X
AE Evaluation	All Encounters				
Medical History	X	_	_	_	_

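### The plan contradicts itself on who uses HPE after week 12, and the analysis would pool continuers and stoppers at weeks 26 and 52 as long-term HPE results

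*Combined protocol and SAP*

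**What the plan says.** The baseline treatment list gives the regimen as "Treatment: Topical HPE twice daily for study duration". Under Visit 2 (week 12), the treatment assessment instead reads "Continuation of topical HPE twice daily on the face and decolletage only as indicated for 20 subjects". The next heading is "Visit 3 and 4: Long-term follow-up at 26- and 52-weeks. Cohort 2 (n= up to 80". The Methods say that interested subjects "will be followed to 26-week and 52-week time points for long-term analysis of topical HPE on facial and decolletage skin per subject preference", and the footnote to Table 1 offers long-term participation to everyone interested.

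The Methods also let people who do not continue the products after week 12 return for photos at 6 and 12 months, and add: "These participants will be given another bottle of the study product". The 2X substudy makes a similar offer, not limited to people who stopped.

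On supply, the baseline list says "A second cosmetic kit will be provided at week 6 visit". Visit 2 then states: "Each subject will receive their second cosmetic kit, which will include gentle cleanser, unscented bar soap, HPETM product, SkinceuticalsTM CE Ferulic serum, sunscreen and moisturizer". Visits 3 and 4 list imaging, photography, jar weighing, log review and questionnaires, but no product.

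The Endpoints section places change in photoaging at weeks 6, 12, 26 and 52 under the primary heading. The Data Analysis Plan names two comparisons, baseline against HPE and HPE against the competitor, with no rule that depends on actual use.

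**The concern.** The stated purpose of weeks 26 and 52 is a long-term analysis of HPE on the face and decolletage. That needs a known exposure at each late visit. The plan gives several incompatible accounts of exposure, and its analysis ignores the difference between them.

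If some of those imaged at week 26 or 52 are no longer applying HPE, a single baseline-versus-HPE comparison averages skin under use with skin after stopping. The result estimates neither. If the effect fades after stopping, the average understates the effect of continued use. If it does not fade, the data cannot show that, because the two states are not reported apart. At stake is the long-term claim; the week-6 and week-12 results are not affected.

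**Working it through.** The plan states no figure for this point, so there is nothing to reproduce. The check sets the passages side by side and then adds two illustrations.

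**Who is on HPE after week 12**

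- Baseline treatment list: twice daily, for the whole study.
- Visit 2: 20 subjects, face and decolletage only.
- Visits 3 and 4: up to 80 followed, with no statement of how many are on product.
- Methods: long-term follow-up by preference, plus optional return of people who stopped.

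These cannot all hold. With 20 continuing and 80 followed, up to 80 - 20 = 60 of those imaged would be off product. If use runs for the study duration in everyone followed, none would be.

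**Effect of pooling (illustration only)**

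Let p be the share of returning participants on HPE, and r the share of the on-product effect that stoppers retain. With the same on-product effect in everyone:

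pooled mean / on-product effect = p + (1 - p) × r

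Take 80 returning (assumption) and r from 0 to 0.5 (assumption):

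| On HPE | p | r = 0 | r = 0.5 |
|---|---|---|---|
| 20 | 0.25 | 25% | 62.5% |
| 40 | 0.50 | 50% | 75% |
| 60 | 0.75 | 75% | 87.5% |
| 80 | 1.00 | 100% | 100% |

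The first row uses the 20 from Visit 2 and gives about 25-63%. The last row is the reading in which everyone continues, with no dilution. The contradiction in the text is therefore the difference between a fourfold dilution at worst and none.

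**Listed supply (illustration only)**

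Kits at weeks 0 and 6 suggest that one kit covers about 6 weeks; this is inferred from the dispensing interval. Counting the kit listed at week 12:

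- to week 26: (26 - 12) / 6 = 14 / 6 = 2.3 kits needed, one listed;
- to week 52: (52 - 12) / 6 = 40 / 6 = 6.7 kits needed, one listed.

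Stopping hand and arm use would stretch a kit. If 50-90% of it had gone on the face and decolletage (assumption), it lasts 6 / 0.9 = 6.7 to 6 / 0.5 = 12 weeks, that is, to about week 18.7 to week 24. Kit contents and kit life are not stated, so these figures show only that the listed supply does not visibly match the follow-up. They do not measure a shortage.

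**The case against.** A reader might infer that participants run out of product soon after week 12, that stoppers are resupplied so the two groups converge, and that weeks 26 and 52 can therefore show neither long-term use nor the course after stopping. The documents do not support this.

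- No passage says that supply ends. Jar weighing and log review at Visits 3 and 4 presume product in use, and the product is described as available over the counter.
- The week-12 kit line repeats the Visit 1 line. It again calls the kit the second and still includes the competitor serum, although continuation there is HPE on the face and decolletage only. It may be carried-over text, and so is a weak basis for counting exactly one kit.
- The bottle's timing and intended use are not given. If it is handed over after the last photo, it affects no image.
- Logs and jar weights could separate on-product from off-product participants, so the late visits are not uninformative by design.

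It can also be said that the course after stopping is not a stated objective, and that the return photos offered to stoppers may not be the endpoint imaging; the Methods do not say.

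All of this stands against the stronger reading. It does not remove the point. VISIA-CR imaging is listed for up to 80 at Visits 3 and 4 while Visit 2 continues HPE in 20, so mixing can arise from the visit lists alone. The plan collects exposure records but never says that they will be used in the analysis.

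**Conclusion.** The point holds in a limited form. The passages on who uses HPE after week 12 conflict, supply after week 12 and the timing of the extra bottle are unspecified, and the stated analysis would count images from continuers and stoppers together as HPE results on an endpoint listed as primary.

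The size is uncertain because the mix is undefined. Under the stated assumptions (80 return, 20 on HPE, stoppers retaining 0-50% of a common effect), the pooled mean is about 25-63% of the on-product effect. If everyone followed continues, it is 100%. The kit ratios of 2.3 and 6.7 rest on an inferred 6-week kit life and equal kits, and should not be quoted as a measured shortfall. The defect is an undefined exposure together with a missing analysis rule, which the sponsor should correct before any long-term claim is made.

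**What to change.** 1. Reconcile the Methods, the baseline treatment list, Visit 2 and Visits 3 and 4 on who continues HPE after week 12. Which schedule to keep is the sponsor's decision.
2. State the supply after week 12 that matches that schedule, correct or confirm the week-12 kit line, and state when the extra bottle is given relative to the 6- and 12-month photos.
3. Add to the Data Analysis Plan that each participant at weeks 26 and 52 is classified as on-product or off-product from the treatment log and jar weights. Fix the look-back period and the criterion for use before the late images are analysed. Have the log record any product bought by the participant and any use of the extra bottle, and keep the weight and number of jars issued so that the weights can be interpreted. Classify on recorded use, not on the mere issue of a bottle.
4. Report the two groups separately, with the number in each, and base any long-term HPE claim on the on-product group only.

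The cost is mainly wording and a small addition to the log, since logs and weights are already collected; extending supply would also use more product. The statistical cost is a smaller on-product group at weeks 26 and 52. That group is self-selected, so its results describe people who chose to continue and should be reported in those terms.
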